#### Quality of Life data

EQ-5D-5L, EORTC QLQ-C30, Skindex-16, FNAE and the Hornheide questionnaire Data collection within 14 days prior to cycles 5, 9, 13,17, 21, 25, 29, 33 and within 6 weeks of final cycle of treatment in the study. Analysis will use EQ-5D-5L Index Scores, EQ-5D-5L VAS and EORTC QLQ-C30, Skindex-16, FNAE and the Hornheide questionnaire domain scores. Absolute means at each assessment point will be compared against baseline. Percentage of respondents experiencing change +/- 0.3 SD and +/- 0.5 SD will be used to assess those experiencing a degree of meaningful substantive change.

#### 11.5 **Missing Data**

In the event that data for an individual patient has not been collected, after the response assessment has taken place but in the absence of an event, a Last-Observation-Carried-Forward analysis will be performed. However, for PRO outcomes any missing data will not be imputed using a last-observation-carried-forward analysis. These data will be compared to baseline using the partially overlapping samples framework and subject to an NMAR (not-missing-at-random) sensitivity analysis if more than 10% of data is missing.

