# 6.5 Procedures for assessing efficacy

6.5.1 Photography of skin lesions and MRI/CT scan of the area encompassing the primary tumour

The primary endpoint ORR will be assessed for externally visible tumour(s) which are

being used as target lesions using **clinical response criteria** (Appendix 2 table 1) according to World Health Organisation (WHO) criteria. This requires photography that shows bi-dimensional measurements (≥10mm in longitudinal dimension and ≥10mm in the perpendicular dimension). If patients only have target lesions being assessed radiologically using MRI/CT scan (target lesion ≥10mm in the longest diameter) ORR will be assessed using **RECIST 1.1 criteria**. Patients who have target lesions measurable by both clinical response criteria and radiologically by RECIST 1.1 will have their outcome assessed using **composite response criteria** (Appendix 2 table 2).

Please see Appendix 1 and Appendix 2 for more information.

The MRI/CT scan and photography must be completed at baseline (within 6 weeks of the first dose of trial treatment) in order to identify the target lesions. Photographs and scans must be sent to the study team for central review within 5 days of assessment. Please refer to the imaging manual for more information.

Objective tumour response to treatment will be assessed after cycle 4 (12 weeks +/-7 days from cycle 1 day 1) and before cycle 5, and then every 12 weeks (+/- 7 days from the previous photography/scan) whilst the patient is on treatment. If the patient stops treatment for any reason other than disease progression target lesions will continue to be assessed every 12 weeks (+/- 7 days) until disease progression for a maximum of 12 months. Photographs and scans must be sent to the study team for central review within 5 days of assessment. Please refer to the imaging manual for more information.

Please refer to Appendix 6 for contingency measures during extenuating circumstances.

Complete response can only be confirmed with clinical biopsy otherwise response remains as partial response.

Baseline	Scan 1	Subsequent scans	End pf treatment and in				
		on treatment	follow up				
Within 6 weeks of Cycle1 Day1	12 weeks (+/- 7 days) from Cycle1 Day1 but before Cycle 5	Every 12 weeks (+/- 7 days) from previous photography/scan	If no progression, photography and MRI/CT scans should continue every 12 weeks (+/- 7 days) from previous				
			photography/scan				

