# 11.1 Sample size calculations

The hedgehog pathway inhibitors (HHIs) have shown an ORR of about 45% in the first line setting. In the ERIVANCE study, the ORR with vismodegib was 42.9% at 9 months follow-up which increased to 47.6% at 21 months follow-up (9). In the BOLT study of sonidegib, the ORR was 47.0% at primary 6 month follow-up, increasing to 56.1% (95% CI: 43.3–68.3) at 18 month follow-up (10). In the second line setting, cemiplimab showed an ORR of 31%, in a recently reported phase 2 study in the 2nd line setting (18), after a median follow-up of 15 months.

Assuming an ORR of cemiplimab to be around 45% at 6-months in the first line setting, this study is powered as a single arm Simon II Stage design. This will be used to differentiate between a poor treatment (success rate of 25%) and a good treatment (success rate 45%) using a nominal significance level alpha = 5% and a power of 80%.

Once 18 patients are recruited, an interim analysis will be performed with the decision rule of progression to Stage II if 6 or more of the 18 patients achieve a response. If ≤5 patients have responded (poor response) or if 15 out of the 18 patients have responded (exceptional response) the trial will be stopped.

Stage II will be the recruitment of a further 19 patients. To account for a potential loss of non-evaluable patients (assuming a 10% drop out rate) the sample size will be inflated to N = 41.

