## Evaluation of best overall response

The best overall response is the best response recorded from the start of the treatment until disease progression/recurrence (taking as reference for PD the smallest measurements recorded since the treatment started). In general, the patient's best response assignment will depend on the achievement of both measurement and confirmation criteria.

The table below provides a summary of the overall response calculation:

Target lesions	Non-Target lesions	New Lesions	Overall response
CR	CR	No	CR
CR	Non-CR/non-PD	No	PR
CR	Not-evaluated*	No	PR
PR	Non-CR/non-PD or	No	PR
	not all evaluated		
SD	Non-CR/non-PD or	No	SD
	not all evaluated		
Not all evaluated	Non-CR/non-PD	No	Not evaluable
PD	Any	Yes or No	PD
Any	PD	Yes or No	PD
Any	Any	Yes	PD

\* When no imaging/measurement is done at all at a particular time point, the patient is not evaluable (NE) at that time point. If only a subset of lesion measurements are made at an assessment, usually the case is also considered NE at that time point, unless a convincing argument can be made that the contribution of the individual missing lesion(s) would not change the assigned time point response.

Patients with a global deterioration of health status requiring discontinuation of treatment without objective evidence of disease progression at that time should be classified as having "symptomatic deterioration". Every effort should be made to document the objective progression even after discontinuation of treatment.

In some circumstances it may be difficult to distinguish residual disease from normal tissue. When the evaluation of complete response depends on this determination, it is recommended that the residual lesion be investigated (fine needle aspirate/biopsy) to confirm the complete response status.

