# Reporting of results

- All patients included in the study must be assessed for response to treatment, even
  if there are major protocol treatment deviations or if they are ineligible. Each patient
  will be assigned one of the following categories: 1) complete response, 2) partial
  response, 3) stable disease, 4) progressive disease, 5) Non-evaluable for response:
  specify reasons (early death, malignant disease; early death, toxicity; tumour
  assessments not repeated/incomplete; other (specify))
- All of the patients who met the eligibility criteria should be included in the main analysis of the response rate. Patients in response categories 4-9 should be considered as failing to respond to treatment (disease progression). Thus, an incorrect treatment schedule or drug administration does not result in exclusion from the analysis of the response rate. Precise definitions for categories 4-9 will be protocol specific.
- All conclusions should be based on all eligible patients.
- Sub-analyses may then be performed on the basis of a subset of patients, excluding
  those for whom major protocol deviations have been identified (e.g., early death due
  to other reasons, early discontinuation of treatment, major protocol violations, etc.).
  However, these sub-analyses may not serve as the basis for drawing conclusions
  concerning treatment efficacy, and the reasons for excluding patients from the
  analysis should be clearly reported.
- The 95% confidence intervals should be provided

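### Carrying the last tumour assessment forward lets ORR and DCR include patients not assessed at the landmark, against Appendix 1 and mainly at 12 and 24 months

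*Protocol*

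**What the plan says.** Section 11.5 covers an individual patient's data that were not collected once the response assessment has taken place. For these, "in the absence of an event, a Last-Observation-Carried-Forward analysis will be performed". The only outcomes taken out of this rule are the patient-reported ones. ORR (6, 12 and 24 months) and DCR (6, 12 and 24 months, Section 2.3) are not exempted, and the rule is not labelled a sensitivity analysis.

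Appendix 1 takes another line. Under Evaluation of best overall response: "When no imaging/measurement is done at all at a particular time point, the patient is not evaluable (NE) at that time point". Under Reporting of results: "All of the patients who met the eligibility criteria should be included in the main analysis of the response rate". That same list makes assessments that were not repeated or were incomplete a non-evaluable category (category 5) and counts categories 4 to 9 as failing to respond.

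Section 11.6 adds a third treatment: patients judged non-evaluable for listed reasons are replaced in the principal analysis.

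Section 6.5.1 sets the assessments at 12 weeks and every 12 weeks after that. When treatment stops for a reason other than progression, they continue "until disease progression for a maximum of 12 months".

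**The concern.** Under carry-forward, a response or stable disease that nobody re-examined is reported as present at a later landmark. Once a patient is no longer imaged, a loss of response can enter only as a recorded event, and progression is less likely to be recorded when lesions are not assessed. Section 7.4 leaves later treatment to the investigator, and starting it is not among the PFS events in Section 2.3. An old status could therefore be carried across a new therapy.

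The 12- and 24-month rates are there to describe durability, and these are the rates most exposed. The primary 6-month ORR is also exposed in principle, because the design leaves almost no slack in its type I error. Three unreconciled rules also leave the numerator and denominator open to choice after the data are known.

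**Working it through.** **1. The rules side by side.** Take a patient with at least one post-baseline assessment, no recorded event and no assessment at the landmark.

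| Source | Treatment of this patient |
|---|---|
| Section 11.5 | last status carried forward: CR/PR stays in ORR and DCR, SD stays in DCR |
| Appendix 1 | not evaluable at that time point; a patient categorised as non-evaluable counts as failing to respond |
| Section 11.6 | possibly replaced, if the reason is on the list and disease is held not to be measurable after treatment |

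These give different numerators or denominators. A patient with no post-baseline assessment is outside Section 11.5.

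**2. What can be carried to 6 months.** Scheduled assessments fall at about weeks 12 and 24. Appendix 2 requires a visible PR or CR to be maintained for at least 4 weeks. Appendix 1 (Confirmation) requires a repeat assessment at least four weeks later. A patient with PR at week 12 and nothing afterwards meets neither, so there is no valid response to carry. Week-12 SD can still be carried into the 6-month DCR.

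**3. What happens at 24 months.** If treatment stops at month t without progression, scheduled imaging ends by about t + 12. For t below 12 this is before month 24. Patients in that group with no progression or death therefore have a 24-month status that can only be imputed. Illustration: if 20% to 30% stop in year 1 without progression (an assumption; the protocol gives no rate), 0.20 × 37 = 7.4 and 0.30 × 37 = 11.1. So at most about 7 to 11 of 37 patients are affected, and fewer once later events are removed.

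**4. Reproducing the design (Section 11.1).** Inputs: p0 = 0.25, p1 = 0.45, alpha 5%, power 80%; "progression to Stage II if 6 or more of the 18 patients achieve a response"; "Stage II will be the recruitment of a further 19 patients", so 18 + 19 = 37. The test is taken as one-sided, as is usual for a Simon design. No final cut-off c is stated. The probability of success is

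P(p) = Σ (x = 6 to 18) Bin(x; 18, p) × P(Y ≥ c − x), with Y ~ Bin(19, p).

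| Cut-off c | P(0.25) | P(0.45) |
|---|---|---|
| 12/37 | 0.1369 | 0.877 |
| 13/37 | 0.0876 | 0.852 |
| 14/37 | 0.0496 | 0.806 |
| 15/37 | 0.0249 | 0.732 |

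Of these, only 14/37 meets both targets. The upper stop at 15 of 18 does not change its figures to four decimals.

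**5. Size of the effect, relative to missing-as-failure.** Each carried response adds 1/37 = 2.7 points. One such patient makes 13 observed responses count as 14, which is a cut-off of 13: type I error 0.088. Two make it a cut-off of 12: 0.137. Both figures change only the final count and leave stage I as it is.

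**6. Cost of missing-as-failure.** Assume missingness m is unrelated to response and replace p by p(1 − m) in both stages, with c = 14.

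| m (assumed) | p1(1 − m) | Power | p0(1 − m) | Type I error |
|---|---|---|---|---|
| 0% | 0.450 | 0.806 | 0.2500 | 0.050 |
| 5% | 0.4275 | 0.728 | 0.2375 | 0.034 |
| 10% | 0.405 | 0.635 | 0.2250 | 0.022 |

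**The case against.** Several objections have force.

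- A reader might infer that any patient with PR at week 12 and no later visit becomes a 6-month responder, and that this could turn a failed primary analysis into a success. The 4-week maintenance and confirmation rules do not support that, and Section 11.5 does not waive them. The alpha figures show sensitivity, not a likely event, and rest on a cut-off that the protocol does not state.
- A reader might infer that every early stopper has an imputed 24-month status. That is wrong. Section 11.5 applies only without an event, lesions are still assessed for up to 12 months after stopping, and deaths are collected to 24 months after treatment.
- A reader might infer that carry-forward overstates the true ORR. It gives a higher figure only relative to missing-as-failure. It also freezes SD as non-response, and the hedgehog-inhibitor rates in Section 11.1 rise with follow-up (42.9% to 47.6%; 47.0% to 56.1%), so a late response could be missed.
- Appendix 1 is the RECIST reference. Its not-evaluable rule works per time point and its failure rule per patient, and it names categories 4 to 9 although only five are listed. Appendix 2, used for visible lesions, has no rule for a missing assessment. If ORR is read as a response achieved by the landmark, an earlier confirmed response counts anyway.
- Missing-as-failure has its own bias at 24 months, where it would fail patients for whom no assessment was planned.

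These points narrow the concern but do not remove it. Category 5 lies within the failure rule however the list is read, the endpoint is worded as ORR at 6 months, and no passage says which rule governs.

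**Conclusion.** The concern holds in a limited form. Followed as written, Section 11.5 lets ORR and DCR include response or disease control that was not observed at the landmark. That conflicts with Appendix 1 and is not reconciled with Section 11.6. The exposure is mainly in the 12- and 24-month rates, where part of the gap comes from the assessment schedule itself. For the 6-month ORR it is small as long as unconfirmed responses are not carried, which the text should say.

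The size is 2.7 points per carried response relative to missing-as-failure. The type I error figures assume the derived 14/37 cut-off and a one-sided test. The number of patients affected cannot be known from the protocol. The rule should be settled before outcome data are seen.

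**What to change.** - In Section 11.5, make the main landmark analysis of ORR and DCR count a patient with no assessment in the landmark window as not responding or not controlled, in line with Appendix 1.
- Keep carry-forward only as a labelled sensitivity analysis, and state that an unconfirmed response is never carried forward.
- State in Section 11.6 how replacement fits with this rule, so that each patient has one defined treatment in the main analysis.
- At 24 months, report how many patients had no scheduled assessment. Base durability on the Kaplan-Meier duration of response and PFS already planned in Section 11.4, censored at the last tumour assessment. Section 11.4 now censors PFS at last follow-up, which may fall after imaging has ended.

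The change is to wording, with no extra visits. The price is lower, conservative rates, most visibly at 24 months, and a loss of power if 6-month assessments are missed: from 0.806 to about 0.73 at 5% missing and 0.64 at 10%, both assumed rates. Complete 6-month assessment therefore matters more under this rule.

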#### 11.6 Non-evaluable patients

In the principal analysis, where a patient is not evaluable, additional patients will be recruited to replace them. Every attempt should be made to obtain disease

assessments for all patients. The TMG will centrally review all patients to determine if any are non-evaluable and need to be replaced.

A patient is considered not evaluable if:

- 1) The patient has not completed any cycles of cemiplimab for one of the following reasons:
  - Death from any cause
  - Withdrawal from trial due to progressive disease
  - Withdrawal from trial for a reason unrelated to drug or disease (e.g. patient preference, administrative reasons)
- 2) Disease cannot be measured after treatment for one of the following reasons:
  - o Death from causes other than basal cell carcinoma
  - Withdrawal from trial for a reason unrelated to drug or disease (e.g. patient preference, administrative reasons)

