#### 4.2 Number of patients

41 patients will be recruited across multiple sites, aiming to recruit 37 evaluable patients.

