#### 11.2 Analysis methods

All analyses will proceed using standard analytical techniques including Kaplan-Meier survival curves. Analysis will include tabulation of baseline characteristics of recruited patients. Intention to treat analysis will be used. Baseline characteristics for those patients not completing trial treatment will be tabulated for comparison with treated patients, to ensure the ability to generalise results. Baseline characteristics will include (but are not limited to) demographic data, tumour stage and grade. Categorical data will be reported as a percentage. Numeric data will be reported as median, mean, range and SD.

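### The replacement rule in section 11.6 takes some early deaths, treatment-related deaths included, out of the primary response rate and conflicts with the intention-to-treat statement in section 11.2

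*Protocol*

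**What the plan says.** Section 11.6 sets the rule for the main analysis: "In the principal analysis, where a patient is not evaluable, additional patients will be recruited to replace them". A patient is non-evaluable in either of two situations.

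- **No cycle of cemiplimab completed**, because of death from any cause, withdrawal from the trial for progressive disease, or withdrawal for reasons unrelated to drug or disease.
- **Disease not measurable after treatment**, because of "Death from causes other than basal cell carcinoma" or, again, an unrelated withdrawal.

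The Trial Management Group reviews patients centrally and decides who is replaced.

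Two other places define the denominator differently. Section 11.2 says "Intention to treat analysis will be used". Appendix 1, under Reporting of results, puts all patients who met the eligibility criteria in the main response-rate analysis. It lists early death from toxicity among the non-evaluable categories, treats such categories as failure to respond, and adds: "All conclusions should be based on all eligible patients".

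On numbers, section 4.2 says "41 patients will be recruited across multiple sites, aiming to recruit 37 evaluable patients". Section 11.1 describes a two-stage Simon design with 18 patients and then 19 more, a poor rate of 25%, a good rate of 45%, alpha 5% and power 80%. The interim step is a "decision rule of progression to Stage II if 6 or more of the 18 patients achieve a response".

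**The concern.** In a single-arm trial the response rate is the whole result, so who is in the denominator matters as much as who responds. A patient who is dosed and dies of an immune-related event before the first response assessment at 12 weeks has not benefited. Under section 11.6 that patient is dropped from the principal analysis and another is recruited. A patient can be removed only if no cycle was completed or no post-treatment measurement exists, so no one with a documented response can leave, while some failures can.

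Two things are at stake. The reported ORR, and the chance of passing both decision points with a poor treatment, become too high. And sections 11.2 and 11.6 cannot both be followed: an analyst must choose a denominator, possibly after seeing what each choice gives. A later analysis plan could not comply with both as written.

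**Working it through.** **1. Which patients leave and which stay**

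| Situation | Under 11.6 |
|---|---|
| No cycle completed, death from any cause | Replaced |
| No cycle completed, withdrawal from the trial for progression | Replaced |
| Non-BCC death before a post-treatment measurement, treatment-related death included | Replaced |
| Unrelated withdrawal, with no cycle completed or no post-treatment measurement | Replaced, but not a treatment failure |
| Progression after a completed cycle | Stays |
| BCC death after treatment (at least one cycle completed) | Stays |
| Drug-related withdrawal | Stays |

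The first three rows create the upward bias. Under intention to treat, all of these patients would stay.

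**2. Reproducing the design**

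Inputs from section 11.1: p0 = 0.25, p1 = 0.45, n1 = 18, continue with 6 or more responders, n = 37. The final cut-off c is not stated. With exact binomial probabilities,

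P(success | p) = Σ over x = 6 to 18 of P(X1 = x) × P(X2 ≥ c − x), where X1 ~ Bin(18, p) and X2 ~ Bin(19, p).

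| c | Type I error at 0.25 | Power at 0.45 |
|---|---|---|
| 13 | 0.0876 | 0.852 |
| **14** | **0.0496** | **0.806** |
| 15 | 0.0249 | 0.732 |

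Only c = 14 meets both stated targets. The upper stop at 15 of 18 does not change these values to four decimals. The margin below 5% is 5.00 − 4.96 = 0.04 percentage points. The inflation also reproduces: 37 × 1.10 = 40.7, rounded to 41, which allows 41 − 37 = 4 non-evaluable patients.

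**3. Effect of replacing failures**

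Assumptions: the true rate over all patients is 25%, k patients are replaced, and all k are non-responders. The rate among the 37 analysed is then q = 0.25 × (37 + k)/37. Put q into the formula above with c = 14. The stage 1 column is P(X1 ≥ 6 | 18, q).

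| k | q | Passing stage 1 | Type I error |
|---|---|---|---|
| 0 | 0.250 | 0.283 | 0.050 |
| 1 | 0.257 | 0.306 | 0.060 |
| 2 | 0.264 | 0.330 | 0.073 |
| 3 | 0.270 | 0.355 | 0.087 |
| 4 | 0.277 | 0.380 | 0.103 |

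**4. Effect on the reported figure**

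Fourteen responders are 14/37 = 37.8% of the evaluable patients. If four non-responders had been replaced, they are 14/41 = 34.1% of all patients. The 95% Wilson intervals are 24.1% to 53.9% and 21.6% to 49.5%.

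**5. Cost of counting unassessed patients as failures**

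Keep 14 of 37, and let m dosed patients have no assessment for reasons unrelated to response. The effective rate is 0.45 × (37 − m)/37. For m = 1 it is 0.438 and power is 76.6%. For m = 2 it is 0.426 and power is 72.1%.

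**The case against.** The rule is narrower than it first appears. A reader might infer that anyone who progresses early is deleted, but the text requires both that no cycle was completed and that the patient withdrew from the trial because of progression. Sections 9.1.1 and 9.2 separate stopping treatment from leaving the trial, and the first scheduled assessment is at 12 weeks in a disease that section 1 calls generally slow growing. Such cases should be rare. This stands.

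A reader might also infer that only failures can leave. That is wrong, because unrelated withdrawals leave too. If they are independent of response, the rate among evaluable patients is unchanged and the type I error stays at 4.96%.

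The 10.3% figure could be taken as the expected size. It is not: it makes every patient in the 10% allowance a drug or disease failure, and nothing in the protocol supports four such events.

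It is tempting to say that inflating to 41 and also replacing patients leaves the final sample size undefined. Sections 4.2 and 11.1 read more naturally as one mechanism, in which the extra four are the replacements. Nor does the protocol propose a 41-patient decision set, so cut-offs for one are not evidence of a fault. An unstated final cut-off may properly sit in the analysis plan.

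Last, Appendix 1 is a RECIST quick reference, refers to categories 4 to 9 after listing five, and leaves precise definitions to the protocol. It supports the point but does not carry it.

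None of this answers the core. Sections 11.2 and 11.6 are both trial-specific and disagree, and treatment-related deaths fall within the wording of 11.6.

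**Conclusion.** The point holds in this limited form. Section 11.6 removes from the principal analysis patients who complete no cycle because of death or withdrawal for progression, and patients who die of a non-BCC cause, treatment-related deaths included, before a post-treatment measurement. Scoring these as failures is what section 11.2 implies, so the ORR under 11.6 is biased upward.

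The likely size is modest but not negligible: about 6.0% type I error with one replaced failure and 7.3% with two, against 4.96% as designed. One such patient is enough to exceed 5%. About 10.3% with four is the upper end. These figures rest on the derived cut-off of 14 in 37, a true all-patient ORR of 25%, and every replaced patient being a non-responder. The direction does not depend on the cut-off; the size does depend on how many failures are removed.

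**What to change.** Amend section 11.6, and word section 11.2 to match:

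- Every eligible patient who received any cemiplimab stays in the principal ORR analysis and in the 18-patient decision. Death, or no post-baseline assessment, counts as non-response.
- Replacement is allowed only for patients never dosed for reasons unrelated to drug or disease. Section 11.2 should name this as the one exception.
- The evaluable set of section 11.6 is reported as a sensitivity analysis.

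Moving the replacement decision to the Independent Data Monitoring Committee would not give a decision-maker without sight of response, since section 13.3 has it oversee efficacy. A fixed rule that leaves little to judge is the better safeguard.

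The change is an amendment to wording, best made before the 18-patient decision. It has a price. Each dosed patient without an assessment lowers the reported ORR by at most 1/37 = 2.7 points. Realised power falls from 80.6% to about 76.6% with one such patient and 72.1% with two, if non-assessment is unrelated to response. The amendment should say so. If several are expected, holding 80% power would need more patients.
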